3.4.2. Baseline Characteristics

Randomization is stratified by the following, as recorded in the Interactive Response Technology (IRT) system:

- Best response to first-line chemotherapy (CR or PR vs. SD)
- Metastatic disease site (visceral vs. non-visceral) at the time of initiating first-line chemotherapy. The ‘non-visceral’ stratum includes patients with locally-advanced disease as well as patients with only non-visceral disease.

The primary analyses of OS will be stratified by these randomization stratification factors.

Other baseline characteristics (including demographics, physical measurements, disease history and prior anti-cancer therapies) are described in [Section 6.5.1](#). These baseline characteristics are not planned to be included as stratification variables or covariates in statistical models unless otherwise specified in [Section 6](#).

3.5. Safety Endpoints

3.5.1. Adverse events

Treatment-Emergent Adverse Events

Treatment-emergent adverse events (TEAEs) are those events with onset dates occurring during the on-treatment period.

On-treatment period is defined as follows:

- Arm A: time from the first dose of study treatment through minimum (30 days + last dose of study treatment, start day of new anti-cancer drug therapy – 1 day)
- Arm B: time from Cycle 1 Day 1 through minimum (30 days + end date of BSC, start day of new anti-cancer drug therapy – 1 day).

As defined in [Section 3.4.1](#), ‘End date of BSC’ is the date of completion or discontinuation as collected in the ‘Disposition - Treatment Phase’ eCRF page.

The start day of new anti-cancer drug therapy after the first dose of study treatment is derived as outlined in [Section 5.2.5](#).

Adverse Events of Special Interest (AESIs)

AESIs are immune-related adverse events (irAE) and infusion-related reactions (IRRs). The criteria for classification of an AE as an irAE or IRR are described in [Appendix 1](#) and [Appendix 2](#), respectively.

3-Tier Adverse Events

It should be recognized that most studies are not designed to reliably demonstrate a causal relationship between the use of a pharmaceutical product and an adverse event or a group of adverse events. Except for select events in unique situations, studies do not employ formal adjudication procedures for the purpose of event classification. As such, safety analyses are generally considered as an exploratory analysis and its purpose is to generate hypotheses for further investigation. The 3-tier approach facilitates these exploratory analyses.

Adverse events and clusters of adverse events, of any causality and treatment-related, will also be summarized following a 3-tier approach. Under this approach, AEs are classified into 1 of 3 tiers.

Tier-1 events: These are pre-specified events or clusters of events of clinical importance and will be described in the Safety Review Plan.

Tier-2 events: These are events that are not Tier-1 but are “common”. A MedDRA PT is defined as a Tier-2 event if it is reported by

- a) at least 10% of patients with any grade in any treatment arm, or
- b) at least 5% of patients with Grade 3, 4 or 5 in any treatment arm.

Tier-3 events: All other AEs that are classified neither as Tier-1 nor Tier-2.

4. ANALYSIS SETS

Data for all patients will be assessed to determine if patients meet the criteria for inclusion in each analysis population prior to releasing the database and classifications will be documented per Pfizer’s standard operating procedures.

Only patients who signed informed consent will be included in the analysis sets below.

[Table 4](#) summarizes the use of the analysis sets for efficacy, safety, baseline characteristics and exposure.

Table 4. Statistical Analyses by Analysis Set

Endpoints	Full Analysis Set	Per Protocol Analysis Set	Safety Analysis Set
Baseline Characteristics	✓		✓
Prior and Concomitant Therapies	✓		✓
Exposure			✓
Efficacy: Primary	✓	✓	
Efficacy: Secondary	✓		
Efficacy: Exploratory	✓		
Safety			✓

4.1. Full Analysis Set

The full analysis set (FAS) will include all randomized patients. Patients will be classified according to the study treatment assigned at randomization.

The FAS will be the primary analysis set for evaluating all efficacy endpoints, PRO endpoints, and patient characteristics within each of the co-primary populations:

- 1) all randomized patients, and
- 2) patients determined to have PD-L1-positive tumors (including infiltrating immune cells) by a verified GMP PD-L1 IHC test; these patients will be identified by a retrospective analysis of the mandatory recent FFPE tumor biospecimen (see Sections 4.1 and 6.1.1 of the study protocol) using an analytically-validated and GMP-verified PD-L1 IHC assay with a pre-specified scoring algorithm defining PD-L1-positive status. The PD-L1 IHC assay and scoring algorithm will be fully defined prior to initiation of sample analysis and will be documented separately.

4.2. Safety Analysis Set

The safety analysis set will include all patients who receive at least one dose of study drug on Arm A or completed C1D1 on Arm B. If a patient randomized to Arm B incorrectly receives avelumab, then the patient will be classified in Arm A for the purpose of safety analyses.

4.3. Other Analysis Set

4.3.1. Per-protocol analysis set

The per-protocol (PP) analysis set is a subset of the FAS and will include patients who do not meet any of the following criteria that could impact the key objectives of the study. Patients who meet any of the following criteria will be excluded from the PP analysis set.

- Patients randomized to Arm A who did not receive at least one dose of avelumab
- Patients randomized to Arm B who were treated with avelumab

- Baseline ECOG status ≥ 2
- Patient does not meet inclusion criteria 1, 2, or 3 and patient meets exclusion criterion 1

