9.2.2. Per-Protocol Analysis Set

The Per-Protocol Analysis Set is a subset of the Full Analysis Set and will include patients who receive at least 1 dose of study treatment or who only receive BSC and do not have major protocol deviations expected to impact the primary objectives of the study. Major protocol deviations will be pre-specified in the SAP. The Per-Protocol Analysis Set will be used for sensitivity analyses for the primary efficacy endpoint.

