3.4. Baseline Variables

3.4.1. Study drug, study treatment and baseline definitions

In this study, ‘study drug’ refers to avelumab or BSC and ‘study treatment’ (or ‘treatment arm’) refers to one of the following:

- Arm A = Avelumab + BSC;
- Arm B = BSC alone.

Start and end dates of study treatment:

- For Arm A:
 - The date/time of first dose of study treatment is the earliest date/time of non-zero dosing of the study drug.
 - The date/time of last dose of study treatment is the latest date/time of non-zero dosing of the study drug.

- For Arm B:
 - The date of start of study treatment is defined as the date of Cycle 1 Day 1 (C1D1); a patient is considered to be treated in Arm B if they complete the C1D1 visit.
 - ‘End date of BSC’ (last dose of study treatment) is the date of completion or discontinuation as collected in the ‘Disposition - Treatment Phase’ eCRF page.

Definition of baseline:

Definition of baseline for efficacy and PRO analyses

The last measurement prior to randomization will serve as the baseline measurement for efficacy and PRO analyses. If such a value is missing (since per protocol the first PRO assessment is planned to occur on Cycle 1 Day 1), the last measurement prior to the first dose of study treatment will be used as the baseline measurement except for analyses of tumor assessments data where the baseline assessment would be considered as missing.

Definition of baseline for immunogenicity analyses (Arm A only)

The last available assessment prior to the start of treatment with avelumab is defined as ‘baseline’ result or ‘baseline’ assessment. If an assessment is planned to be performed prior to the first dose of avelumab in the protocol and the assessment is performed on the same day as the first dose of avelumab, it will be assumed that it was performed prior to avelumab administration, if assessment time point is not collected or is missing.

Definition of baseline for safety analyses

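### The per-protocol set drops Arm A patients who never started avelumab but keeps Arm B patients who never started, so the exploratory OS sensitivity analysis selects on treatment start in one arm only (minor)

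*SAP*

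**What the plan says.** SAP 4.1 sets the starting population: "The full analysis set (FAS) will include all randomized patients". SAP 4.3.1 then defines the PP set by a list of exclusions: "Patients who meet any of the following criteria will be excluded from the PP analysis set". Two criteria on that list are specific to an arm:

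- Arm A: "Patients randomized to Arm A who did not receive at least one dose of avelumab"
- Arm B: "Patients randomized to Arm B who were treated with avelumab"

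The remaining criteria concern baseline ECOG status and eligibility, not treatment start.

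Elsewhere the SAP does define a start for Arm B. In SAP 3.4.1, "a patient is considered to be treated in Arm B if they complete the C1D1 visit". The safety set in SAP 4.2 applies a start rule to both arms: "all patients who receive at least one dose of study drug on Arm A or completed C1D1 on Arm B".

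Protocol 9.2.2 words the PP set as "patients who receive at least 1 dose of study treatment or who only receive BSC", subject to there being no major deviations.

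The PP set is used to repeat the OS analysis (Protocol 9.3 and 9.3.1; SAP Table 4 and 6.2.2.2). SAP 6.2.2.2 classes the sensitivity analyses as exploratory.

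**The concern.** An Arm A patient who is randomized and never dosed leaves the PP set. An Arm B patient who is randomized and never completes C1D1 stays in it. The two arms of the PP comparison are therefore no longer selected by the same rule.

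In an open-label trial, not starting can follow from early deterioration or from knowing the allocation, so non-starters may differ in prognosis from starters. SAP 6.2.2.2 lists two modified repeats of the primary analysis, PP and unstratified. Only the PP repeat changes the population. What is at stake is how far agreement between the PP and full-set results can be read as evidence of robustness.

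**Working it through.** **Step 1. Is there a gap in the text?** The treatment-start rules compare as follows.

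| Set | Arm A non-starter | Arm B non-starter |
|---|---|---|
| Full analysis set (SAP 4.1) | in | in |
| Safety set (SAP 4.2) | out | out |
| PP set (SAP 4.3.1) | out | in |

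Only the PP set treats the arms differently, and no other section adds an Arm B start criterion to it. SAP 6.5.2.1 cross-tabulates randomized against treated patients with a category for no treatment, so untreated patients are foreseen.

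**Step 2. Design figures (not in dispute).** Schoenfeld's formula for 1:1 allocation is events = 4(z_alpha + z_power)² / (ln HR)².

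- All patients (HR 0.7, one-sided alpha 0.015, power 93%): 4(2.170 + 1.476)² / 0.1272 = 418 events. Power at 425 events is 93.4%, against 93% stated.
- PD-L1-positive (HR 0.65, one-sided alpha 0.01, power 80%): 217 events. Power at 219 events is 80.5%, against 80% stated.

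The PP definition does not affect these figures.

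**Step 3. How large could the shift be?** The documents give no non-start share and no prognosis for non-starters. Both are assumed here: a share q, the same in each arm, and a death hazard m times that of starters. With 668/2 = 334 patients per arm, q = 1% is about 3 patients per arm and q = 5% about 17.

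A bound at a true HR of 1: at time zero the ratio of average hazards, with non-starters removed from Arm A only, is 1/(1 + q(m − 1)). This gives 1/1.01 = 0.990 for q = 1%, m = 2, and 1/1.10 = 0.909 for q = 5%, m = 3. The Cox HR lies closer to 1 because the high-risk non-starters die early and leave the risk set.

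Large-sample Cox simulation (exponential OS, control median 12 months, 28 months' accrual taken as uniform, cut-off at month 39), true HR 1:

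| q | m | Full set | PP as written | PP, both arms excluded |
|---|---|---|---|---|
| 1% | 2 | 0.9994 | 0.9931 | 0.9991 |
| 2% | 2 | 0.9993 | 0.9870 | 0.9994 |
| 5% | 2 | 0.9993 | 0.9685 | 0.9987 |
| 5% | 3 | 0.9995 | 0.9562 | 0.9987 |
| 5% | 1 | 0.9994 | 0.9994 | 0.9987 |

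A repeat run gave about 0.995 (1%, m = 2) and 0.955 (5%, m = 3). Simulated trials of 668 patients cut at 425 events gave 0.978 (3%, m = 2) and 0.952 (5%, m = 3).

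With a true HR of 0.70 in starters and no benefit in non-starters, PP as written gives 0.6949 (1%, m = 2) to 0.6701 (5%, m = 3). Excluding in both arms gives 0.699 in each case.

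**Step 4. Size against sampling error.** The standard error of log HR at 425 events is about √(4/425) = 0.097. The shift is |ln 0.9931|/0.097 = 0.07 standard errors in the mildest case with m above 1 and |ln 0.9562|/0.097 = 0.46 in the most extreme.

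**Step 5. When does it vanish?** With m = 1 there is no shift. If Arm B non-starters withdraw consent at once, they are censored almost at randomization and contribute practically nothing, which is nearly the same as excluding them.

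**The case against.** The strongest case for leaving the text alone has five parts.

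- **The rule has a rationale.** Best supportive care is not a discrete product. Departing from assignment means getting no avelumab in Arm A and getting avelumab in Arm B, and the two arm-specific criteria are exactly those cases. Protocol 9.2.2 has no C1D1 condition. This stands in part: the protocol does not require the C1D1 rule. But the SAP itself uses C1D1 completion to say when an Arm B patient is treated.
- **The window is short.** Study treatment must start within 3 days of randomization (Protocol 5.1), and entry requires ECOG 0 or 1 and a life expectancy of at least 3 months (Protocol 4.1). Non-starters are probably few. This stands, and it favours the low end of the range.
- **The symmetric rule is not guaranteed unbiased.** Take a true HR of 1, with 5% frail patients at twice the hazard in each arm. Let all frail Arm B patients but only 20% of frail Arm A patients fail to start. PP as written then gives 0.994 and the symmetric PP 1.025. At three times the hazard the figures are 0.991 and 1.036. This stands, under its own assumed inputs. It is a limit of any set that selects after randomization, and it does not justify a one-arm rule.
- **Counts are already planned.** SAP 6.5.2 and 6.5.2.1 give the number in each analysis set by arm, and the randomized-versus-treated table. Only the reason for PP exclusion would be new.
- **The analysis is exploratory.** This stands, and it limits the weight of the point.

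A reader might infer that the PP result must favour avelumab, or that the trial's positive result is inflated. The documents support neither. The direction depends on non-starters' prognosis, follow-up and frequency by arm, none of which is given. The primary test uses all randomized patients, and Protocol 1.2.3.3 reports that the primary objective was met at the interim analysis of that test.

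**Conclusion.** The asymmetry is in the current SAP text and is certain; its size is not. If non-starters have a worse prognosis, are followed for death and are similarly frequent in both arms, the PP HR leans slightly towards avelumab. At a true HR of 1 the lean is roughly 0.5 to 1% at the mild end (1% non-starters, twice the hazard) and about 4.5% at the severe end (5%, three times). All of those inputs are assumptions. Even the severe case is under half a standard error of the log HR in the large-sample calculation. Type I error, the event targets, the primary OS analysis and the trial's conclusion are untouched. Severity: minor.

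**What to change.** Add one exclusion to SAP 4.3.1: *Patients randomized to Arm B who did not complete the Cycle 1 Day 1 visit*. This brings the PP set into line with SAP 3.4.1 and 4.2. Give the reason for each PP exclusion alongside the per-arm counts already planned in SAP 6.5.2.1.

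If the PP analysis has already been run, report the symmetric version beside it, labelled as added later. Protocol 1.2.3.3 still foresees a final OS update, where this could be done.

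The cost is one line of text and a few fewer Arm B patients in the PP set. The symmetric set can still be biased if the reasons for not starting differ between arms, so it should stay supportive to the full analysis set.

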1.6. Patient Discontinuation

- Required in-clinic visits, including Avelumab administrations, may be missed without causing discontinuation from the maintenance treatment phase of the study. However, all study patient withdrawal criteria listed in Protocol [Section 6.5](#) remain applicable.
- For study patient discontinuation reporting in the CRF: select the most appropriate status for discontinuation; if the discontinuation is associated with the current COVID-19 pandemic, enter “COVID-19” in the “Specify Status” field.

- It's important to continue to enter the CRF data as quickly as possible, so we have access to the data for safety monitoring. If the sponsor determines that the impact of COVID-19 on protocol visits and procedures and associated timeframes needs to be reported on a case report form (CRF), this will be requested.

17. SUPPLEMENT 1: CROSSOVER FROM BSC ALONE (ARM B) TO AVELUMAB PLUS BEST SUPPORTIVE CARE

This supplement provides details for patients in the BSC alone arm who crossover to receive avelumab plus BSC. All other information in the protocol not addressed in this supplement still apply. After 60 days following the final OS update or approval of Amendment 6, whichever is later, no additional Arm B patients will be allowed to crossover to avelumab plus BSC.

ELIGIBILITY CRITERIA

Inclusion Criteria

Patients randomized to Arm B must meet all of the following inclusion criteria to be eligible to crossover from BSC alone to avelumab plus BSC:

1. Patients randomized to Arm B (BSC alone) ongoing in the maintenance phase (ie, patients must not have completed the EOT visit).
2. Patients without progressive disease while on study as per RECIST v1.1 guidelines as assessed by the investigator.
3. Evidence of a signed and dated informed consent document indicating that the patient (or a legally acceptable representative, as allowed by local guideline/practice) has been informed of the aspects of crossover.
4. Patients who are willing and able to comply with scheduled visits, treatment plans, laboratory tests, and other study procedures.
5. Eastern Cooperative Oncology Group (ECOG) performance status (PS) 0 or 1 ([Appendix 1](#)).
6. Adequate bone marrow function, including:
 - a. Absolute neutrophil count (ANC) $\geq 1,500/\text{mm}^3$ or $\geq 1.5 \times 10^9/\text{L}$;
 - b. Platelets $\geq 100,000/\text{mm}^3$ or $\geq 100 \times 10^9/\text{L}$;
 - c. Hemoglobin ≥ 9 g/dL (may have been transfused).

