1. VERSION HISTORY

This Statistical Analysis Plan (SAP) for study B9991001 is based on the protocol amendment 4 dated 28-Mar-2019.

Table 1. Summary of Major Changes in SAP Amendments

Version	Version Date	Summary of Changes
1	23-Dec-2015	Not applicable (N/A)
2	02-Apr-2019	
Section 2.1 “Study Objectives”, Section 3.3 “Exploratory Endpoints”, Section 6.3 “Other Endpoints” updated to remove irRECIST objectives and endpoints as per protocol amendment 4.
 
Section 2.2 “Study Design” was updated to reflect changes made in protocol amendment 3.
 
Section 3.2.2 “Efficacy endpoints” – corrected the definition of disease control to include best overall response (BOR) of non-CR/non-PD to take into account patients without measurable disease at baseline; clarified the criterion for SD must have been met at least 6 weeks after the date of randomization as per protocol.
 
Section 3.4.1 “Study drug, study treatment and baseline definitions” – added definition of end date of study treatment; added definition of baseline for immunogenicity analyses; removed definition of baseline for ECG assessments as no summaries will be provided (ECGs are only collected post-treatment if clinically indicated).
 
Section 3.4.2 “Baseline characteristics” – updated the stratification factor from “Best response to first-line chemotherapy per BICR assessment” to “Best response to first-line chemotherapy” to reflect changes made in protocol amendment 3.
 
Section 3.5.1 “Adverse events” – updated the definition of treatment-emergent adverse events; clarified that start of new anti-cancer drug therapy is used in the definition of on-treatment period.
 
Section 4.2 “Safety Analysis Set” – clarified that patients randomized to Arm B that incorrectly received avelumab will be classified in Arm A for the purpose of safety analyses.
 
Section 4.3.1 “Per-protocol analysis set” – updated the definition of PP analysis set to align with the key inclusion/exclusion criteria.
 
Section 5.1.2 “Decision rules” – added description of primary analysis of OS; updated Table 6 to reflect correct simulated operational characteristics of the study design and added a footnote to clarify that the actual interim and final analyses will occur at the same calendar time for both patient populations.
 
Section 5.2.5 “Definition of start of new anti-cancer drug therapy”, Section 5.2.6 “Definition of start of new anti-cancer therapy”, Section 5.2.10 “Adequate baseline tumor assessment” and Section 5.2.11 “Adequate post-baseline tumor assessment” were added to provide the details associated with derivations used to define the on-treatment period and to implement censoring in efficacy analyses.
 
Section 5.2.7 “Definition of on-treatment period” – clarified that start of new anti-cancer drug therapy is used in the definition of on-treatment period.
 
Section 5.3.2.4 “Exposure” – clarified that in imputation derivations the cutoff date is used as last dosing date in the analyses of patients that have study drug ongoing at the time of the cutoff date.
 
Section 5.3.3.1 “Date of last contact” – added withdrawal of consent date in the

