6.2.2.2. Sensitivity analyses for overall survival

The following sensitivity analyses will be performed to explore the robustness of the primary analysis results for OS. These analyses are regarded as purely exploratory. The sensitivity analyses will repeat the primary analysis (p-value, HR and 95% CIs) described in Section 6.1.1.1 with the modifications below:

- PP analysis set
- unstratified

Methods for evaluating the validity of model assumptions

The proportional hazards assumption will be checked visually by plotting $\log(-\log(\text{OS}))$ versus $\log(\text{time})$ within each randomization stratum.

Schoenfeld residuals for the stratified Cox proportional regression model will be plotted to investigate graphically violations from the proportional hazards (PH) assumption; a non-zero slope is evidence of departure from PH. The PH assumption will be formally tested using Schoenfeld's residual test (Schoenfeld, 1980; Therneau and Grambsch, 2000). Large departures from PH will be evidenced by a p-value <0.05 .

If these show large departures from proportional hazards, then OS assessment will also be analyzed based on restricted mean survival time (RMST) differences (Zhang, 2013).

Restricted Mean Survival Time (RMST)

The hazard ratio estimate from the Cox proportional hazard model is routinely used to empirically quantify the between-arm difference under the assumption that the ratio of the two hazard functions is constant over time. When this assumption is plausible, such a ratio estimate may capture the relative difference between two survival curves. However, the clinical meaning of such a ratio estimate is difficult, if not impossible, to interpret when the underlying PH assumption is violated (ie, the hazard ratio is not constant over time).

The RMST is a robust and clinically interpretable summary measure of the survival time distribution. Unlike median survival time, it is estimable even under heavy censoring. There is a considerable body of methodological research (eg, Royston and Parmar, 2011; Uno, Wei, et al, 2014; Zhang, 2013) about the use of RMST to estimate treatment effects as an alternative to the hazard ratio approach.

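### SAP 4.3.1: an *and* keeps patients who fail only inclusion criterion 1 or 2 in the per-protocol set, and the Arm B rule would remove permitted crossover patients if the per-protocol OS analysis is repeated at the final OS update

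*SAP*

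**What the plan says.** Protocol 9.2.2 describes the PP set as "patients who receive at least 1 dose of study treatment or who only receive BSC and do not have major protocol deviations" that could affect the primary objectives, and leaves the list to the SAP: "Major protocol deviations will be pre-specified in the SAP".

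SAP 4.3.1 supplies that list as four rules, any one of which removes a patient. In short they are:

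- Arm A without a dose of avelumab;
- "Patients randomized to Arm B who were treated with avelumab";
- baseline ECOG of 2 or more;
- "Patient does not meet inclusion criteria 1, 2, or 3 and patient meets exclusion criterion 1".

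The neighbouring SAP 4.2, on the safety set, is narrower about avelumab in the control arm: "If a patient randomized to Arm B incorrectly receives avelumab".

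By its version history the SAP "is based on the protocol amendment 4 dated 28-Mar-2019". Amendment 5 later allowed Arm B patients to cross over. Protocol Supplement 1 limits this to patients still in the maintenance phase, and its second inclusion criterion is "Patients without progressive disease while on study as per RECIST v1.1 guidelines as assessed by the investigator". Protocol 1.2.3.3 plans a final OS update at 425 deaths overall and 219 in the PD-L1-positive population.

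SAP 6.2.2.2 repeats the primary OS analysis on the PP set and says of the sensitivity analyses: "These analyses are regarded as purely exploratory".

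**The concern.** The PP analysis is there to show whether the OS result depends on patients who should not have been in the trial or did not get the assigned treatment. Two of its rules do not define that set.

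**Eligibility rule.** The four rules are already alternatives, but inside the last one the inclusion failures are tied to exclusion 1 by *and*. Patients who fail a key entry criterion without progressing stay in the set meant to exclude them. Agreement between the full analysis set (FAS) and PP then says less than it appears to. This affects every PP run.

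**Arm B rule.** Under Amendment 4 any avelumab in Arm B was an error, so the rule was adequate when written. Since Amendment 5 it also covers permitted crossover. Removing those patients conditions one arm, and only that arm, on a post-randomization event that requires survival. This tilts the hazard ratio (HR) towards avelumab even with no treatment effect. It matters only if PP is repeated at the final OS update.

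**Working it through.** **1. The eligibility rule**

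The four conditions, from Protocol 4.1 and 4.2:

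- I1: diagnosis, stage IV, measurable disease before chemotherapy.
- I2: regimen, 4 to 6 cycles, last dose 4 to 10 weeks before randomization.
- I3: no progression after first-line chemotherapy.
- E1: progression on or after first-line chemotherapy.

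I1 and I2 do not depend on progression; I3 and E1 are close to mirror images. As written, a patient leaves if (fails I1 or I2 or I3) **and** (meets E1). The alternative is (fails I1 or I2 or I3) **or** (meets E1).

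| Pattern | Removed as written | Removed with *or* |
|---|---|---|
| Fails I1 only | no | yes |
| Fails I2 only | no | yes |
| Fails I1 and I2, not E1 | no | yes |
| Fails I3, E1 not recorded | no | yes |
| E1, no inclusion failure recorded | no | yes |
| Fails I3 and meets E1 | yes | yes |

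Over all 2 × 2 × 2 × 2 = 16 patterns the two readings differ in 8: the seven with an inclusion failure and no E1, plus E1 alone. A progressor is normally recorded under both I3 and E1 and is removed either way, so in practice the gap is I1 and I2. SAP 6.5.2.2 reports protocol deviations but does not alter the PP set.

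**2. The Arm B rule**

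The stated design reproduces. With power = Φ(√D/2 × |ln HR| − z):

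- All patients: √425/2 × 0.3567 − 2.170 = 1.507, power 93.4% (stated 93%).
- PD-L1-positive: √219/2 × 0.4308 − 2.326 = 0.861, power 80.5% (stated 80%).

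With the two-look boundaries these become 93.1% and 80.2%, and the interim limits are 2.595 and 2.947, as in SAP Table 5.

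The mechanism shows in the death fractions. With a 12-month control median the monthly hazard is ln 2/12 = 0.0578. A patient alive at crossover, *g* months before cut-off, dies by cut-off with probability 1 − exp(−0.0578*g*): 0.21 for 4 months, 0.37 for 8, 0.53 for 13. At 425 deaths among 668 with no effect, the overall fraction is 425/668 = 0.64. The rule therefore takes low-mortality patients out of Arm B.

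Size was obtained by simulation, 1,500 runs per setting.

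- From the documents: 334 per arm (668/2), control median 12 months, 28-month non-uniform accrual, cut at the 425th death.
- Assumed: exponential survival, linearly rising accrual rate, no drop-out, crossover patients drawn at random from living Arm B patients, no effect of crossover on survival.
- Assumed crossover: 3%, 5% or 10% of Arm B (10, 17 or 33 of 334).
- Assumed gap from crossover to cut-off: SAP Table 6 plans 7 to 8 months from interim to final (29 to 36, 31 to 39). Amendment 5 (13 February 2020) to Amendment 6 (08 March 2021), which still treats the update as future, is about 13 months. Four months represents late crossover, since Supplement 1 keeps crossover open until after the update.

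Ratio of PP HR to FAS HR, with the resulting PP HR in brackets (true HR × ratio):

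| Gap | True HR | 3% | 5% | 10% |
|---|---|---|---|---|
| 4 months | 1.0 | 0.966 (0.97) | 0.942 (0.94) | 0.886 (0.89) |
| 8 months | 1.0 | 0.977 (0.98) | 0.960 (0.96) | 0.919 (0.92) |
| 13 months | 1.0 | 0.982 (0.98) | 0.970 (0.97) | 0.937 (0.94) |
| 4 months | 0.70 | 0.961 (0.67) | 0.933 (0.65) | 0.867 (0.61) |
| 8 months | 0.70 | 0.971 (0.68) | 0.950 (0.67) | 0.901 (0.63) |
| 13 months | 0.70 | 0.982 (0.69) | 0.970 (0.68) | 0.938 (0.66) |

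A repeat run at HR 1.0 agreed to within 0.003. Uniform accrual changed little: 0.968/0.946/0.891 at 4 months and 0.977/0.960/0.920 at 13.

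A variant with uniform accrual and crossover at the 315th death gave, at true HR 1, mean HRs of 0.952 and 0.907 with 17 and 33 patients removed. The rejection rate of an unstratified test at one-sided 0.015 rose from 1.5% to 4.9% and 12.3%.

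**The case against.** **The *and* may only join a list of reasons.** The lead-in treats the rules as alternatives, and the version history says the definition was revised to match the key eligibility criteria. That is probably the intent. It supports the correction: the text does not deliver its stated aim, and set membership has to be determined from the text before database release.

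**A PP repeat at the update is not clearly planned.** The objective was met at the interim, and Protocol 1.2.3.3 does not mention PP at the update. This stands, and the second part is conditional on it. The condition is realistic, though. SAP 6.2.2.2 repeats the primary analysis on PP, SAP 5.1.2 times that analysis at 425 and 219 deaths, and neither document drops PP at the update.

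**Protocol 9.2.2 can be read either way.** Study treatment there includes avelumab plus BSC and BSC alone, so a crossover patient may satisfy its first limb; or its BSC-only limb governs Arm B and the SAP rule follows it. This too stands, and is why the two documents need reconciling.

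**The size is assumed and its extreme is unlikely.** The values 0.89 and 0.61 need 10% crossover with everyone crossing 4 months before cut-off. At 13 months the figures are 0.98 to 0.94 and 0.69 to 0.66. This is fair; the direction does not depend on these choices.

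**Conclusion.** The concern holds.

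Read literally, the eligibility rule leaves patients who fail only inclusion 1 or 2 in the PP set at every PP run. The documents do not say how many patients this affects, so its effect on any estimate is unknown.

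The Arm B rule is a problem only if PP is repeated at the final OS update. Under the assumed crossover numbers and dates, a true HR of 1.0 would appear as about 0.98 to 0.89 and a true HR of 0.70 as about 0.69 to 0.61, always in avelumab's favour. The simulation covers all randomized patients, not the PD-L1-positive population. It does not model the progression-free requirement at crossover, which would be expected to add to the selection.

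The FAS analysis and the alpha are untouched. The Arm B problem cannot touch the interim result, which came before any permitted crossover. The PP analysis is exploratory, so this is a wording correction worth making and not a threat to the primary conclusion.

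**What to change.** - Split the last rule of SAP 4.3.1 into two separate exclusions: fails inclusion criterion 1, 2 or 3; meets exclusion criterion 1.
- Limit the Arm B rule to avelumab received in error, that is, other than by crossover under Protocol Supplement 1, and state that crossover patients stay in Arm B in the PP set.
- Clarify Protocol 9.2.2 to match, since its BSC-only wording does not cover permitted crossover.
- Alternatively, state that no PP analysis is planned at the final OS update. The Arm B rule can then stay as it is.

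An analysis that censors at crossover is optional and not part of this correction.

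The cost is wording in SAP 4.3.1 and a clarification in Protocol 9.2.2. After the split the PP set becomes slightly smaller, because it also loses patients randomized outside the 4-to-10-week window of inclusion 2a; the documents do not give that number.
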